**Study Synopsis**

Sponsor	Vergent Bioscience, Inc. [REDACTED]
Title	A Phase 2, Open-label Study to Evaluate the Safety and Efficacy of VGT-309, a Tumor-Targeted, Activatable Fluorescent Imaging Agent, to Identify Cancer in Subjects Undergoing Lung Cancer Surgery
Protocol Number	VGT-309-2-2021USA
Principal Investigator	[REDACTED]
Study Centers	[REDACTED]
Investigational Medicinal Product (IMP)	VGT-309 for Injection, 10 mg/vial
Primary Efficacy Objective	Identification of the proportion of subjects with at least one Clinically Significant Event (CSE) as defined by: [REDACTED] [REDACTED] [REDACTED]
Safety Objective	To determine the safety and tolerability of VGT-309 when used as a fluorescent imaging agent in subjects with suspected or proven lung cancer
Secondary Efficacy Objectives	To evaluate the sensitivity, specificity, positive predictive value (PPV) and negative predictive value (NPV) of VGT-309 to detect cancer utilizing near-infrared (NIR) fluorescence and histopathology results.
Introduction and Rationale	[REDACTED] [REDACTED]

Primary Endpoints - Efficacy	The proportion of subjects with at least one Clinically Significant Event (CSE) as defined by: [REDACTED] [REDACTED] [REDACTED] [REDACTED]
Safety Endpoints	Assessment of clinical laboratory tests, physical exam results, ECGs and vital signs measurements at various time points during the study, and documentation of treatment-emergent adverse events
Secondary Endpoints - Efficacy	
 
1. Sensitivity [REDACTED] [REDACTED] [REDACTED]
 
2. Specificity [REDACTED] [REDACTED] [REDACTED]
 
3. Positive predictive value (PPV) [REDACTED] [REDACTED] [REDACTED]
 
4. Negative predictive value (NPV) [REDACTED] [REDACTED] [REDACTED]
 
 
* TP = true positive, FP = false positive, TN = true negative, FN = false negative

Study Population	A total of 40 subjects scheduled to undergo standard of care surgical resection for a lung nodule that is suspected or proven to be lung cancer will be enrolled to ensure at least 38 evaluable subjects.

	
[REDACTED]
 
[REDACTED]
 
[REDACTED]

Inclusion Criteria	
In order to be enrolled in the study the subject must:
 
 
1. Be willing and able to sign the informed consent and comply with study procedures.
 
2. Be between the ages of 18 and 85, inclusive.
 
3. Be male or female and meet the following conditions:             
 
a. Female participants must be of non-childbearing potential, or,
 
b. If of childbearing potential be non-pregnant or non-lactating and agree to use highly effective contraception from screening through Day 30.
 
c. Male participants, if not surgically sterilized, and if engaging in sexual intercourse with a female partner of childbearing potential, must be willing to use highly effective contraception from screening through 30 days post-dose and agree not to donate semen during this waiting period.
 
d. Highly effective contraception involves the use of a condom for the male, plus one of the following for the female:                     
 
• Oral, injectable, implantable, intravaginal, or transdermal hormonal contraceptives, or
 
• Intrauterine device or intrauterine hormone-releasing system
 
• NOTE: Participants who abstain from heterosexual intercourse as their usual and preferred lifestyle, will not be required to use contraception as described above. They are required to maintain abstinence from screening through Day 30.
 
 
 
 
 
4. Have a lung nodule or mass that might be considered primary lung cancer or lung metastases, whether or not it is biopsy-proven.
 
5. Be scheduled to undergo standard of care surgical resection for a lung nodule or mass with diagnostic and/or curative intent and meet all pre-operative surgical and anesthesia acceptance criteria.
 
6. Have acceptable kidney and liver functions at study entry as evidenced by:
 
[REDACTED]
 
[REDACTED]
 
7. Have an ECOG score of 0-2.
 
8. Meet all standard surgical and general anesthesia requirements.
 
9. Have not participated in a clinical trial within the last 30 days.
 

Exclusion Criteria	
The subject may not be enrolled in the study if:
 
 
1. They are not a candidate for standard of care surgery based on opinion of the surgeon, anesthesiologist, or other consulting physician.
 

	
2. They have a known allergy or reaction to ICG, other radiographic contrast agent, or any component of VGT-309.
 
[REDACTED]
 
4. They are prisoners, institutionalized individuals, or are unable to consent for themselves.
 
5. Have any other co-morbidity or habit that the Investigator believes will interfere with their ability to comply with and complete the study.

Study Methodology and Design	
This is a Phase 2, open-label study to evaluate the safety and efficacy of VGT-309, a tumor-targeted, activatable fluorescent imaging agent, to identify cancer in subjects undergoing lung cancer surgery. A total of 40 subjects will be enrolled to ensure at least 38 evaluable subjects with the option to expand enrollment by protocol amendment if deemed necessary to meet primary and/or secondary objectives.
 
Following agreement with and signing of the informed consent, subjects will undergo screening measurements for the study. Assessments include the following, unless they have been done within 4 weeks prior to the anticipated dosing:
 
 
1. Medical, surgical and medication history.
 
2. Complete physical exam, including vital signs and weight.
 
3. Standard pre-operative chemistry, hematology, coagulation and urinalysis clinical laboratory studies.
 
4. 12-lead ECG.
 
5. Serum pregnancy test for females of child-bearing potential.
 
 
[REDACTED]
 
[REDACTED]
 
Following surgery, subjects will be monitored for safety during their hospitalization. After discharge from the hospital, and approximately 14 days post-surgery, the subjects will be contacted by telephone to assess their well-being. Between 19 to 39 days post-surgery, subjects will either return to the clinic or participate in a telehealth visit for final safety assessments. If there are no adverse events requiring further follow up, subjects will then be released from the study.
 
If a subject chooses to withdraw from the study prior to the final visit, they will be asked to undergo a final safety assessment before their departure.

VGT-309 Description	
[REDACTED]

Primary Efficacy Assessments	█ [REDACTED] █ [REDACTED] █ [REDACTED]
Secondary Efficacy Assessments	█ [REDACTED]
Safety Assessments	

• Treatment-emergent adverse events.

• Clinical laboratory assessments of blood and urine:

◦ Hematology – Standard panel

◦ Coagulation – INR and APTT

◦ Chemistry – Standard panel including liver function tests (LFTs) and amylase

• Pre- and post-dose ECGs.

• Vital signs (BP, HR, temp, resp).

• Additional studies if identified during the trial as being necessary to adequately assess safety.

Statistical Methods and Considerations	
Sample Size:
 
[REDACTED]
 
Efficacy:
 
A descriptive analysis of the baseline subject and tumor characteristics will be performed. Quantitative data will be presented as a standard set of summary statistics (n/mean (standard deviation)/median/minimum/maximum). Categorical data will be expressed as frequency (%).
 
For the primary endpoint analysis, the proportion of subjects undergoing NIR imaging with at least 1 CSE will be identified and
 
[REDACTED]
 
[REDACTED]
 
[REDACTED]
 
[REDACTED]
 
[REDACTED]

[REDACTED]

All data analyses will be performed for all subjects as a group.

**Safety:**

Adverse event (AE) data will be listed by subject. Treatment-emergent adverse events (TEAEs), serious adverse events (SAEs), and AEs leading to study drug discontinuation will be summarized by treatment group, system organ class, and preferred term using the current version of the Medical Dictionary for Regulatory Activities (MedDRA).

Listings of individual subject laboratory results will be provided. Laboratory results and change from baseline for selected lab tests will be summarized by treatment at scheduled visits.

Twelve-lead ECGs and vital signs measurements will be listed by subject and summarized by incidence of events/abnormalities or descriptive statistics as appropriate. Individual data for physical examination findings, prior and concomitant medications and medical history will be provided.

**List of Abbreviations:**

AE	Adverse Event
ALP	Alkaline Phosphatase
ALT	Alanine Aminotransferase
APTT	Activated Partial Thromboplastin Time
AR	Adverse Reaction
AST	Aspartate Aminotransferase
BP	Blood Pressure
BUN	Blood Urea Nitrogen
CFR	Code of Federal Regulations
CT	Computed Tomography
eCRF	Electronic Case Report Form
CTCAE	Common Terminology Criteria for Adverse Events
DSC	Data Safety Committee
ECG	Electrocardiogram
EDC	Electronic Data Capture
FDA	Food and Drug Administration
GEE	Generalized Estimating Equation
GCP	Good Clinical Practice
GGT	Gamma-glutamyl-transferase
GLP	Good Laboratory Practice
GMP	Good Manufacturing Practice
Hgb	Hemoglobin
IB	Investigator's Brochure
ICF	Informed Consent Form
ICH	International Conference on Harmonization
INR	International Normalized Ratio
IRB	Institutional Review Board
ITT	Intent-to-treat
IV	Intravenous
kg	kilogram
L	Liter
LDH	Lactate Dehydrogenase
LFT	Liver Function Test
MedDRA	Medical Dictionary for Regulatory Activities
mg	milligram
mL	Milliliter
NIR	Near-infrared (imaging)
NOAEL	No-Observed-Adverse-Effect-Level
PI	Principal Investigator
PK	Pharmacokinetic
RBC	Red Blood Cell
ROC	Receiver Operating Characteristic
SAE	Serious Adverse Event
SD	Sprague-Dawley (rats)
SUSAR	Suspected Unexpected Serious Adverse Reaction
TC	Total cholesterol
TG	Triglyceride

## 1. INTRODUCTION

A comprehensive review of VGT-309 is contained in the Investigator's Brochure supplied by the Sponsor, Vergent Bioscience, Inc. The Investigator's Brochure should be reviewed prior to initiating the study.

### 1.1 Background and Rationale

Non-small cell lung cancer is a particularly lethal cancer, for which the best opportunity for cure comes from early detection and complete resection at surgery. Great advances in minimally invasive surgery (robotics; video-assisted thoracic surgery) have provided the opportunity to reduce the impact of major lung resection on the subject with lung cancer.

This has come at the cost of increasing difficulty in localizing small cancers deep in the lung parenchyma due to the elimination of the ability to palpate the lung through a large thoracotomy incision. Currently this is overcome by one of three methods: - a) remove a larger amount of tissue than required for biopsy of a suspicious lesion; b) wait until a suspicious lesion has grown sufficiently to allow easier detection at surgery; or c) perform a thoracotomy.

None of these options is optimal. The first, because a large amount of lung may be unnecessarily removed if the lesion is not cancer; the second, because the opportunity for early curative surgery may be missed if the cancer spreads in the months waiting for it to grow further; and the third negates the proven benefit of minimally invasive surgery.

The use of a tumor-targeted, activatable fluorescent imaging agent that can be taken up and bound by cancer tissues and visualized by tumor-specific fluorescence under NIR light during the surgical procedure would solve this problem if the drug readily identified the lesion for the surgeon. This could allow early and well-targeted surgical biopsy and subsequent appropriate cancer surgery for the correctly identified population.

### 1.2 Nonclinical *In Vitro* and *In Vivo* Experience

**1.2.1 Genotoxicity**

[REDACTED]

**1.2.2 Safety Pharmacology**

Single dose safety pharmacology studies showed no specific CNS, respiratory, or

**1.2.3 Local Tolerance**

[REDACTED]

**1.2.4 Single Dose Toxicity in Sprague-Dawley Rats and Beagle Dogs**

[REDACTED]

[REDACTED]

[REDACTED]

[REDACTED]

**1.2.5 VGT-309 NIR imaging of Lung Tumors in Dogs**

[REDACTED]

The image consists of a series of horizontal bands. The majority of the image is black. There are several white horizontal stripes of varying widths. The first stripe is relatively narrow. Subsequent stripes are wider and appear at regular intervals. The widths of the stripes create a stepped or layered effect across the image. The image has a high-contrast, grainy texture, characteristic of a scan of a physical document or a specific type of film. The overall effect is abstract and geometric.

Refer to the Investigator's Brochure for further details.

## 2. STUDY OBJECTIVE AND ENDPOINTS

## 2.1 Objectives:

### 2.1.1 Primary Efficacy Objective:

Identification of the proportion of subjects with at least one Clinically Significant Event (CSE) as defined by:

**CONFIDENTIAL**

**2.1.2 Secondary Efficacy Objective:**

- To evaluate the sensitivity, specificity, positive predictive value (PPV) and negative predictive value (NPV) of VGT-309 to detect cancer utilizing near-infrared (NIR) fluorescence and histopathology results.

**2.1.3 Safety Objective:**

- To determine the safety and tolerability of VGT-309 when used as a fluorescent imaging agent in subjects with suspected or proven lung cancer.

**2.2 Endpoints:**

**2.2.1 Primary Efficacy Endpoints:**

The proportion of subjects with at least one Clinically Significant Event (CSE) as defined by:

**2.2.2 Secondary Efficacy Endpoints:**

1. Sensitivity
2. Specificity
3. Positive predictive value (PPV)
4. Negative predictive value (NPV)

\* TP = true positive, FP = false positive, TN = true negative, FN = false negative.

#### 2.2.4 Safety Endpoints:

- Clinical laboratory tests.
- Physical exam results.
- 12-lead ECGs.
- Vital signs measurements.
- Documentation of treatment-emergent adverse events

### 3. STUDY DESIGN

This is a Phase 2, open-label study to evaluate the safety and efficacy of VGT-309, a tumor-targeted, activatable fluorescent imaging agent, to identify cancer in subjects undergoing lung cancer surgery. [REDACTED]

Following agreement with and signing of the informed consent, subjects will undergo screening and baseline measurements for the study. Assessments include the following unless they have been done within 4 weeks prior to the anticipated dosing:

1. Medical, surgical and medication history.
2. Complete physical exam, including vital signs, height and weight.
3. Standard pre-operative chemistry, hematology, coagulation and urinalysis clinical laboratory studies.
4. 12-lead ECGs.
5. Serum pregnancy test for females of child-bearing potential.

Following clearance of all enrollment criteria, each subject will receive an IV administration of [REDACTED] VGT-309 at 12-36 hours prior to surgery (See Section 4 – Study Drug – VGT-309). Upon dosing, subjects will be observed for up to 2 hours and asked about possible treatment emergent adverse events.

Subjects will undergo surgical resection as planned and within the time specified following VGT-309 dosing. Measurements of efficacy will be taken during surgery and during the pathological examination of all surgical specimens.

Following surgery, subjects will be monitored for safety during their hospital stay. After discharge from the hospital, and approximately 14 days post-surgery, the subjects will be contacted by telephone to assess their well-being. Between 19 to 39 days post-surgery, subjects will either return to the clinic or participate in a telehealth visit for final safety assessments. If there are no adverse events requiring further follow up, subjects will be released from the study.

If a subject chooses to withdraw from the study prior to the final visit, they will be asked to undergo a final safety assessment before their departure.

### 4. STUDY DRUG – VGT-309

VGT-309 will be administered as an IV infusion over 15 to 20 minutes. Following are details related to VGT-309 preparation, packaging and labeling and storage. Additional details will be supplied in the Pharmacy Manual.

#### 4.1 VGT-309 Description

VGT-309 will be supplied in a lyophilized form in 5ml vials containing 11mg of VGT-309.

[figure not shown]

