#### 4.2 VGT-309 Proposed Dose

The dose for this study is 0.32mg/kg of VGT-309.

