#### 4.3 VGT-309 Preparation

VGT-309 is stored frozen and must be thawed at room temperature for at least 30 minutes but not more than 2 hours before it is prepared for dosing.

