#### 4.5 VGT-309 Storage and Accountability

VGT-309 will be stored frozen (-25 to -15°C) in a secure, locked area under the responsibility of the clinical research unit pharmacy or its designee.

The Investigator or Investigational Pharmacy must maintain accurate records of the receipt of all study drug, including date received, lot number, amount received, condition of the package and the disposition. Dispensing records will be maintained including the date and amount of study drug dispensed and the identity of the subject receiving the study drug.

Following dosing, all empty vials will be retained until reconciliation with the dispensing and shipping records is complete. Empty vials may then be destroyed using investigative pharmacy policy.

Following final reconciliation, unused study drug may either be destroyed according to site guidelines or returned to Vergent Bioscience, Inc., or designee.

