#### 4.6 VGT-309 Packaging and Labeling

Labels will be in compliance with all applicable regulatory requirements for the labeling of active pharmaceutical ingredients according to Annex 13 of GMP. Specifically, labels will contain:

- “Limited by Federal Law to Investigational Use” statement.
- Study Drug name, route of administration and amount of VGT-309 in the vial.
- Lot number.

- Storage conditions.
- Sponsor name (Vergent Bioscience, Inc).
- Manufacturer.

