#### 7.1.2. Exposure to Study Drug

Extent of exposure to study drug will be summarized for the safety population. [REDACTED]

[REDACTED]

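### Do the two vial contents in the protocol, 10 mg in the synopsis and 11 mg in Section 4.1, put the weight-based dose or any analysis in doubt?

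*Protocol*

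**What the plan says.** The Study Synopsis identifies the investigational product as "VGT-309 for Injection, 10 mg/vial". Protocol Section 4.1 states "VGT-309 will be supplied in a lyophilized form in 5ml vials containing 11mg of VGT-309". Both are current text.

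The dose is set by weight in Protocol Section 4.2: "The dose for this study is 0.32mg/kg of VGT-309". Section 4.3, as far as it can be read, covers thawing only; no concentration, diluent volume, overfill or withdrawable amount is visible. Section 4 says "Additional details will be supplied in the Pharmacy Manual".

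Three other places could use a content figure:
- Section 4.6 lists among the label items "Study Drug name, route of administration and amount of VGT-309 in the vial", without giving a number.
- Section 4.5 says "Dispensing records will be maintained including the date and amount of study drug dispensed", without naming a unit.
- SAP Section 7.1.2 says "Extent of exposure to study drug will be summarized for the safety population"; the method that follows is blacked out.

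**The concern.** The product is a powder that has to be made up, and the amount each subject receives is scaled to body weight. Somewhere between the mg/kg dose and the syringe, someone may need to know how much drug a vial holds. The protocol offers two answers that differ by a tenth, and the legible text does not say that one is a nominal strength and the other a fill.

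If the two figures were a real conflict, and a pharmacy worked from the wrong one, the subject would receive something other than the dose in Section 4.2. The mg/kg figure attached to the trial's results would then be inaccurate for that subject. Dispensing records and any exposure summary in mg could carry the same error. In a study of 40 subjects at a single stated dose, that would be worth knowing.

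**Working it through.** **Inputs.** Vial content 10 mg (Study Synopsis, product row); vial content 11 mg (Protocol Section 4.1); dose 0.32 mg/kg (Protocol Section 4.2). Neither content is derived from other figures in the documents, so there is no calculation of the plan's own to reproduce.

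**Step 1: size of the difference.** 11/10 = 1.10, so 11 mg is 10.0% above 10 mg. 10/11 = 0.909, so 10 mg is 9.1% below 11 mg.

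**Step 2: does either content contradict the dose?** The target amount is 0.32 × weight. For an assumed 70 kg subject this is 0.32 × 70 = 22.4 mg. Vial content does not enter the formula, so the target is the same under either figure.

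**Step 3: worst case for delivered dose, as illustration only.** Three conditions must all hold: the figures are not a nominal strength and a fill; a preparation uses the wrong one; and the powder is made up in a fixed volume, so that the assumed concentration scales with the assumed content. Then:
- vial holds 11 mg, preparation assumes 10 mg: 0.32 × 11/10 = 0.352 mg/kg (+10.0%);
- vial holds 10 mg, preparation assumes 11 mg: 0.32 × 10/11 = 0.291 mg/kg (-9.1%).

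If any one condition fails, the shift is zero. The documents establish none of the three.

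**Step 4: can both statements be true?** The synopsis entry is a product name followed by a strength. Section 4.1 describes the supplied vial and what is in it. A labelled strength and a physical content are different quantities and may differ without either being wrong. The legible text neither confirms nor excludes this reading.

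**Step 5: where would an explanation sit?** The synopsis row describing the drug is blacked out. A figure directly after the Section 4.1 sentence is not reproduced. The Pharmacy Manual and the vial label are outside the documents. The lack of a visible explanation is therefore weak evidence that none exists.

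**Step 6: which analyses depend on vial content?** The safety and efficacy populations (Protocol Table 01; SAP Sections 6.3.2 and 6.3.3) admit subjects with exposure of any size, so membership cannot change. Protocol Section 10.3 analyses all subjects as one group. The proportion with a clinically significant event counts subjects. Sensitivity, specificity, PPV and NPV come from fluorescence and histology classifications. No visible formula among these uses individual dose or mg per vial, and the planned 40 enrolled and 38 evaluable subjects do not depend on it either. The one possible link is the exposure summary, whose method cannot be read.

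**The case for a change.** The strongest opposing case is that a protocol should give one content per vial or say how two figures relate, and this one visibly does neither. Reference to a Pharmacy Manual for further details does not remove a difference between two parts of the protocol itself. If the label carries a single number, it will disagree with one of the two passages. For an intravenous drug dosed by weight, a 10% difference in stated content deserves an explanation, and a clarifying clause costs almost nothing.

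Much of this stands. Both figures are legible and current, the arithmetic is right, and no visible sentence links them. Asking the sponsor to reconcile the synopsis and Section 4.1 with each other, the label and the Pharmacy Manual is reasonable.

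What does not stand is the step from two numbers to a defect in the plan. Nothing shows that either number is wrong, that a pharmacist would prepare a dose from the synopsis row, or that any dose would be misprepared. Nor would it be safe to require a single figure throughout the dispensing record and the exposure summary. Drug dispensed and drug administered are different quantities, and if one number is a strength and the other a fill, each record could properly use a different one.

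**Conclusion.** This is a clerical query. The synopsis and Protocol Section 4.1 give contents that differ by 1 mg and should be reconciled with each other, the label and the Pharmacy Manual; no view is taken here on which figure is right. The dose of 0.32 mg/kg is not contradicted, no dosing error is shown, and the primary and secondary efficacy calculations, the analysis populations and the sample size are unaffected.

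The shifts of +10.0% and -9.1% bound the conditional case in Step 3 for an affected subject; they are not expected errors. The conclusion assumes that the Pharmacy Manual and label give pharmacies a clear content for preparation, which cannot be checked from these documents. If they do not, the matter is one of drug handling for the sponsor to settle and would still leave the visible statistical methods as they are.
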